3.4 Randomization

N/A

4 STUDY ENDPOINTS AND COVARIATES

4.1 PK Endpoints

- Insulin C_{\max} (maximum observed concentration after correction for baseline)
- Insulin $AUC_{0-t_{\text{last}}}$ (area under the baseline-corrected concentration-time curve from time 0 to the last measurable concentration)
- Insulin t_{\max} (time to C_{\max})
- Insulin apparent clearance (CL/F)
- Insulin apparent volume of distribution (V_{ss}/F)
- Fumaryl diketopiperazine (FDKP) elimination half-life ($t_{1/2}$)
- Insulin AUC (area under the serum concentration versus time curve extrapolated to infinity according to the following equation:

$$AUC = AUC_{\text{last}} + C_{\text{last}}/\lambda_z$$

4.2 Safety Endpoints

- Adverse events, serious adverse events, treatment-emergent adverse events
- Adverse Events of Special Interest (AESI), which include the following events:
 - Acute bronchospasm
 - Verified Clinically relevant decline in pulmonary function
 - Hypersensitivity reactions, including anaphylaxis, which can occur with insulin products, including AFREZZA[®]
 - Diabetic ketoacidosis
- Vital sign measurements

Version Date: 17-Jan-2020

- Abnormal clinical laboratory assessments
- Hypoglycemia: asymptomatic, symptomatic, nocturnal, and severe hypoglycemia according to the 2014 International Society for Pediatric and Adolescent Diabetes guideline (3)
- Anti-insulin antibodies

4.3 Predetermined Covariates and Prognostic Factors

N/A

5 DEFINITIONS

5.1 Study Day 1

Study Day 1 is defined as the date of the first study dose.

5.2 Baseline

Baseline values are defined as the last measurements collected on or prior to Study Day 1 before dosing, unless otherwise specified.

5.3 Relative Day

Relative days will be calculated as follows only when the full assessment date is known; partial dates will have missing relative days:

- For days on or after Study Day 1:

$$\text{Relative Day} = \text{Date of Assessment} - \text{Study Day 1} + 1$$

- For days prior to Study Day 1:

$$\text{Relative Day} = - (\text{Study Day 1} - \text{Date of Assessment})$$

5.4 Study Period

Two study periods are defined: an approximately 4-week titration period (Visit 2 – Visit 16, including PK assessments at Day 1) followed by an optional 52-week extension period (Visit 17 – Visit 29). Participants in the titration period are defined as subjects who take at least one dose of study drug in the titration period and participants in the extension period are defined as subjects who complete the titration period and opt to participate in the extension study.

Start date of the titration period is defined as Study Day 1. For subjects who do not participate in the extension period, end date of the titration period is defined as the last visit/contact date; for

subjects who participate in the extension period, end date of the titration period is defined as the date of Visit 15.

Start and end date of the extension period are defined for subjects who participate in the extension period only. Start date is defined as date of Visit 15 +1 day, and end date is defined as the last visit/contact date.

5.5 Study Drug Exposure

For each subject, information regarding study drug exposure will be derived from the eCRF and study drug dosing eDiary data. Here is a summary:

- First dose date is defined as the date the first study drug dose is taken, as shown in the eCRF ('AFREZZA[®] dosing' page at Visit 2).
- Last dose date is defined as the date the last study drug dose is taken, as shown in the eDiary.
- Period-specific treatment start date:
 - Treatment start date in the titration period is defined as Study Day 1.
 - Treatment start date in the extension period is defined for subjects who participate in the extension period only, as the date the first study drug dose is taken after the date of Visit 15.
- Period-specific treatment end date:
 - Treatment end date in the titration period is defined as:
 - The date the last study drug dose is taken, for subjects who do not participate in the extension period;
 - The date the last study drug dose is taken prior or on the date of Visit 15, for subjects who participate in the extension period
 - Treatment end date in the extension period is defined for subjects who participate in extension period only, as the date the last study drug dose is taken.
- Total Exposure time (days) is defined as last study dose date – first study dose date +1.
- Period-specific exposure time (days) is defined as period-specific treatment end date – period-specific treatment start date +1.
- Total daily dose is defined as the sum of all doses of AFREZZA[®] taken during a day.
- Prandial dose at a meal is defined as the sum of the pre-meal dose and the post-meal dose given at that meal. Per protocol, subjects should take a dose at beginning of each meal, and the post-meal dose will be given as needed to keep the blood glucose level in control.

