5 STUDY OBJECTIVES

The objectives of the study, MKC-TI-155 Part 1, are to:

- Assess the safety and tolerability of AFREZZA® in children ages 4 to 17 years with T1DM
- Assess PK following a prandial dose of AFREZZA® in children ages 4 to 17 years with T1DM
- Assess the ability to titrate the prandial and supplemental doses of AFREZZA® at each meal using postprandial SMBG values obtained 120 to 150 minutes after each prandial dose of AFREZZA® in children ages 4 to 17 years with T1DM

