8.1.4 Dose titration

AFREZZA® should be taken at the beginning of the meal. An individualized postprandial dose will be administered 120 to 150 minutes after the initial dose if the SMBG exceeds 180 mg/dL. For dose titration, initial doses for lunch and dinner on Day 1 will also be determined based on the conversion table (Figure 1).

Throughout the study, doses for each of the following 3 days' meals will be titrated at the end of the current 3-day period based on the median SMBG (120 to 150 minutes post-dose) (Table 2). In other words, the subject will measure his/her 120 to 150 minute post-lunch SMBG for 3 days. The median dose (not the average dose, but the middle – between highest and lowest - of the 3 test values) will be used for dose adjustment per Table 2. This new dose should be used for the next 3 days. This process will be duplicated for both the post breakfast and dinner SMBG values.

Table 2 Recommended AFREZZA dose adjustments

Median 120-150 minute PPG value (mg/dL)	AFREZZA dose adjustment for that meal
<110	Decrease dose by 4 units
110-180	Maintain current dose
>180	Increase dose by 4 units

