2 STUDY OBJECTIVES

The objectives of the study, MKC-TI-155 Part 1, are to:

- Assess the safety and tolerability of AFREZZA[®] in children ages 4 to 17 years with T1DM
- Assess PK following a prandial dose of AFREZZA[®] in children ages 4 to 17 years with T1DM

- Assess the ability to titrate the prandial and supplemental doses of AFREZZA[®] at each meal using postprandial self-monitored blood glucose (SMBG) values obtained 120 to 150 minutes after each prandial dose of AFREZZA[®] in children ages 4 to 17 years with T1DM

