8.4.2 Extent of Study Drug Exposure

Detailed dosing information of AFREZZA[®] will be collected from the first dose to the last dose through the trial. Information of doses given during the PK Visit is captured on the eCRF, while other dosing information is captured on the eDiary.

Table Presentation

Dosing information at the PK Visit will be summarized by cohort, and presented in a subject-level listing.

For total exposure time, both numerical and categorical summaries will be provided by cohort and study period. For AFREZZA[®] doses collected on the eDiary, the following will be derived and summarized by cohort. For Cohort 1 and Cohort 2, additional summaries will be provided by starting dose, as appropriate.

- Average total daily dose of AFREZZA[®] at weekly intervals for the titration period, and at monthly intervals for the extension period. For each time interval, only data collected in the 2nd half of the interval (i.e., within 3 days prior to the each clinic visit in the titration period and within 2 weeks prior to each visit in the extension period) will be included in the summary. If a visit is performed, the actual visit date will be used to determine the time frame; if a visit is not performed, the target visit date will be used to determine the time frame. Average total daily dose is defined as the average of all total daily doses taken within a time frame. For each time interval, average total daily dose will be calculated for each subject first, and then summarized by cohort.
- Average prandial dose of AFREZZA[®] by meal at weekly intervals for the titration period, and at monthly intervals for the extension period, calculated using the same method as described above

Moreover, the use of post-meal (i.e., supplemental) doses will be presented in a summary table, by cohort and study period. Both subject-level summary (number and percentage of subjects

taking at least one post-meal dose) and dose-level summary (e.g., number of post-meal doses indicated, number of doses given, etc.) will be provided.

Graphic Presentation

Average total daily dose of AFREZZA[®] and average prandial dose of AFREZZA[®] by meal will be plotted over time to illustrate dose change throughout the study.

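### SAP 5.5 folds the follow-on dose into the prandial dose, so no listed output shows the titrated pre-meal dose by meal

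*SAP*

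**What the plan says.** The third objective (Protocol Section 5, repeated in SAP Section 2) is to "Assess the ability to titrate the prandial and supplemental doses of AFREZZA" at each meal, using glucose self-measured 120 to 150 minutes after each prandial dose. Protocol 8.1.4 sets the rule: "Throughout the study, doses for each of the following 3 days' meals will be titrated at the end of the current 3-day period". The action column of its Table 2 is headed "AFREZZA dose adjustment for that meal": down 4 units, unchanged, or up 4 units, according to the median post-dose reading. Protocol 8.1.5 treats the follow-on dose as a further dose, decided on a reading taken after the prandial dose.

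SAP 5.5 uses the term differently: "Prandial dose at a meal is defined as the sum of the pre-meal dose and the post-meal dose given at that meal". SAP 8.4.2 then plans "Average prandial dose of AFREZZA" by meal, at weekly intervals in the titration period. Appendix 3 lists this as Table 14.1.2.6, Table 14.1.2.6.1 (by starting dose, Cohorts 1 and 2) and Figure 14.1.1.2. The two endpoint lists in SAP Section 4 are "4.1 PK Endpoints" and "4.2 Safety Endpoints"; neither has a titration item.

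**The concern.** Table 2 acts on the dose taken at the start of the meal. To describe how titration went, one first needs that dose, by meal, over time. The SAP instead reports it added to a second dose that is given for a different reason and under a different rule. A rise in the sum may mean that the meal dose was raised, or that it stayed put and follow-on doses were added. A flat sum may mean that nothing changed, or that a follow-on dose was replaced by a larger meal dose.

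This matters in two places. Protocol 6.2 lets the sponsor or DMC decline to proceed to the next age cohorts on titration data as well as safety and PK. Protocol 4.2 says that Part 1 will help set the age range and recommended dosing for Part 2.

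**Working it through.** No figure in the plan needs reproducing here. The check compares the definitions, then tests what the combined dose hides and what the other outputs recover.

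**1. The term in each document.**
- Protocol Section 5 and 8.1.5: the 120 to 150 minute reading follows the prandial dose, and the follow-on dose depends on that reading. The prandial dose is therefore the mealtime dose only.
- SAP Section 2 repeats the objective, "Assess the ability to titrate the prandial and supplemental doses of" the product, and SAP 8.4.2 equates post-meal with supplemental. With the 5.5 definition, the supplemental dose would sit inside the prandial dose and be named again beside it. The conflict is thus within the SAP, and does not depend on the SAP citing Amendment 2 while the protocol supplied is Amendment 3.

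**2. What the sum identifies.** Let P be the pre-meal dose, F the post-meal dose and S = P + F. The by-meal outputs show the change in S, which is the change in P plus the change in F. The change in P follows only if the change in F is known for the same meal and week.

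**3. Illustration.** Doses are assumed, in units per meal, with three identical meals a day.

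| Case | Week 1 (P+F) | Week 4 (P+F) | S per meal | P per meal | Daily F |
|---|---|---|---|---|---|
| A: meal dose raised, follow-on dropped | 8+4 | 12+0 | 12 → 12 | 8 → 12 | 12 → 0 |
| B: no change | 8+4 | 8+4 | 12 → 12 | 8 → 8 | 12 → 12 |
| C: meal dose held, follow-on added | 8+0 | 8+4 | 8 → 12 | 8 → 8 | 0 → 12 |
| D: meal dose raised, no follow-on | 8+0 | 12+0 | 8 → 12 | 8 → 12 | 0 → 0 |

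A cannot be told from B by S, nor C from D. With partial use, a child held at 8 units whose follow-on use grows from none to 4 units at half of meals shows 8 + 0.5 × 4 = 10 units, a rise of 2/8 = 25% with no change in the titrated dose. If that use is constant throughout, S is flat at 10 and there is no spurious rise.

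**4. What the other listed outputs recover.**
- *Figure 14.1.1.3* (daily post-meal dose over time) separates all four cases; see the last column. If it covers the same days and subjects as the dose tables, subtraction gives the mean pre-meal dose: in A, (36 − 12)/3 = 8, then (36 − 0)/3 = 12; in C, (24 − 0)/3 = 8, then (36 − 12)/3 = 8. It does not work by meal. If S is 12, 8 and 8 at the three meals and the daily F is 4, then P could be 8, 8, 8, or 12, 4, 8, or 12, 8, 4. SAP 8.4.2 does not describe this figure, so its time window is not stated.
- *Table 14.4.3.1* (post-prandial glucose by meal, weekly averages per subject) uses the reading that drives Table 2. It is taken before that meal's follow-on dose, so it reflects the pre-meal dose. It shows averages, whereas Table 2 works on a 3-day median, and an average can lie between 110 and 180 mg/dL when individuals do not: (80 + 220)/2 = 150.
- *Table 14.1.2.7* (subjects using post-meal doses; doses indicated and given) is specified by cohort and study period, not by week or meal.
- *Listings:* Appendix 3 has no listing of diary doses; the dose listing covers the PK visit only.

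**5. What the DMC receives.** Appendix 3 marks Tables 14.1.2.6, 14.1.2.6.1 and 14.1.2.7. It does not mark Figure 14.1.1.3 or Table 14.4.3.1. The DMC thus sees the combined dose by meal and week, and follow-on use only pooled over the period.

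**The case against.** The best defence is that the SAP does address titration. Follow-on use has its own table and figure, and post-prandial glucose by meal is the variable that Table 2 acts on. The study is single-arm and descriptive, meant to gain initial experience. Follow-on dosing is an intended part of the regimen (Protocol 4.1), sites may prescribe it regularly from 7-point profiles (Protocol 9.2.6.3), and the objective covers both doses. On that view the total dose per meal is a legitimate summary. The table shells are in separate files, and the Table 14.1.2.6 shell may already split the dose.

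Most of this stands. It rules out any claim that the outputs say nothing about titration, and it is a good reason to keep the sum. It does not justify labelling the sum as the prandial dose, or leaving the pre-meal dose by meal unreported. An objective that covers both doses is better served by showing both. A split inside a shell would ease the reporting problem but would then disagree with the SAP 5.5 definition.

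**Conclusion.** The concern holds in a limited form. SAP 5.5 departs from the protocol's use of the term, and the listed by-meal dose outputs cannot tell a titrated meal dose from new follow-on use. Titration can be judged only indirectly, and less well in the DMC package than in the final report. How far the sum will mislead cannot be computed from the documents, since it depends on how much follow-on use changes during the four weeks; the 25% above is an illustration that assumes growth from none. PK and safety results are unaffected.

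A reader might infer more, without support in the documents:
- *That the titration objective has no result that could answer it.* Table 14.1.2.7, Figure 14.1.1.3 and Table 14.4.3.1 give descriptive evidence.
- *That follow-on use means titration is failing.* The protocol presents it as part of the regimen.
- *That 110 to 180 mg/dL is the plan's success range.* In Table 2 it is only the band in which the dose is left unchanged.
- *That the SAP wrongly dropped a titration endpoint.* The protocol's own list contains only PK and safety endpoints, and the SAP follows it.

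The conclusion about outputs rests on the titles in Appendix 3 and the text of SAP 8.4.2.

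**What to change.** 1. In SAP 5.5, define pre-meal (prandial) dose and post-meal (supplemental) dose separately, and give their sum another name, such as total meal dose.
2. In Tables 14.1.2.6 and 14.1.2.6.1 and Figure 14.1.1.2, show pre-meal dose, post-meal dose and their sum by meal and week. Both tables are already marked for the DMC, so the split reaches it without a new output.
3. Bring the shells into line with the new definitions.
4. Reconcile the follow-on trigger, on which the count of doses indicated in Table 14.1.2.7 depends: Protocol 8.1.4 words it as above 180 mg/dL and 8.1.5 as 180 mg/dL or more.
5. Optionally, add the proportion of subjects, by meal and cohort, whose 3-day median post-dose reading before Visit 15 falls in Table 2's no-change band. This is descriptive only and should not be called a success criterion. With 14 subjects it would be imprecise: 10 of 14 is 71%, with an exact 95% interval of 42% to 92%.

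The cost is a short SAP revision and extra rows in two tables and one figure, from diary data already collected. The sample size and study conduct do not change.

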5.6 Change from Baseline

Change from Baseline = Values at specified post-baseline visit – baseline value

5.7 Incidence Rate

- For analyses based on the entire study, incidence rate = Number of subjects with a specific event / Total number of subjects in analysis population
- For period-specific analyses, incidence rate = Number of subjects with a specific event occurred in the study period / Total number of subjects in analysis population who participant in the study period.

5.8 Event Rate – Observation Time-Adjusted Frequency

- For analyses based on the entire study, Event Rate = Number of events occurred during the entire study/ Total observation time in the entire study in subject-year (or subject-month). For period-specific analyses, Event Rate = Number of events occurred in the study period/ total observation time in the study period in subject-year (or subject-month)
- Event Rate in a time interval = Number of events occurred during the time interval/ Total observation time in the time interval in subject-year (or subject-month)
- Total observation time in subject-year = Sum of observation time (in days) over all applicable subjects in the analysis population/ 365.25. Observation time could be calculated for the entire study, for a study period, or for a time interval, depending on the specific analysis.
- Total observation time in subject-month = Sum of observation time (in days) over all applicable subjects in the analysis population/ 30.4375.
- For different types of events, i.e., adverse events or hypoglycemic events, observation time is defined differently (see corresponding sections for more details).

5.9 Age

For each subject, age will be defined as: Age (in years) = (date of informed consent form (ICF) signed – birth date +1)/365.25, and round down to the first decimal place.

5.10 BMI

BMI at a given visit will be calculated as

Weight (in kg) measured at this visit/height (in m) measured at screening ².

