1 FLOW CHARTS

1.1 STUDY FLOW CHART FOR PK AND TITRATION PHASE

Phase	Screening	PK	Titration period													End of Titration	Follow-up	Early Termination ^a
			3	4	5	6	7	8	9	10	11	12	13	14				
Visit number	1	2	3	4	5	6	7	8	9	10	11	12	13	14	15	16		
Day	D-21 to D-7	D1	D2	D4	D6	D8	D10	D12	D15	D17	D19	D22	D24	D26	D29	D36		
Visit window (days)			0	± 1	± 1	± 1	± 1	± 1	± 1	± 1	± 1	± 1	± 1	± 1	± 1	± 3		
Visit at clinical site	X	X				X			X			X			X	X	X	
Telephone contact			X	X	X		X	X		X	X		X	X				
Informed consent/Assent	X																	
Review inclusion/exclusion criteria	X	X																
Enrollment	X																	
Medical/ surgical history	X																	
Demography	X																	
HbA1c	X														X		X	
Fasting serum C-peptide	X																	

Phase	Screening	PK	Titration period														End of Titration	Follow-up	Early Termination ^a
			3	4	5	6	7	8	9	10	11	12	13	14	15	16			
Visit number	1	2	3	4	5	6	7	8	9	10	11	12	13	14	15	16			
Day	D-21 to D-7	D1	D2	D4	D6	D8	D10	D12	D15	D17	D19	D22	D24	D26	D29	D36			
Visit window (days)			0	± 1	± 1	± 1	± 1	± 1	± 1	± 1	± 1	± 1	± 1	± 1	± 1	± 3			
Serology test ^b	X																		
Full physical examination including Tanner stage, body weight and height, body temperature	X																		
Abbreviated physical examination, body weight		X				X			X			X			X	X	X		
Vitalsigns	X	X				X			X			X			X	X	X		
12-lead ECG	X																		
Urine drug screen, alcohol breath, or plasma test	X																		
Urine cotinine	X	X				X			X			X			X	X	X		
Urine β-HCG (females of childbearing potential) ^c	X	X				X			X			X			X	X	X		
Spirometry (FEV ₁) ^d	X	X							X						X	X	X		

Phase	Screening	PK	Titration period														End of Titration	Follow-up	Early Termination ^a
			3	4	5	6	7	8	9	10	11	12	13	14	15	16			
Visit number	1	2	3	4	5	6	7	8	9	10	11	12	13	14	15	16			
Day	D-21 to D-7	D1	D2	D4	D6	D8	D10	D12	D15	D17	D19	D22	D24	D26	D29	D36			
Visit window (days)			0	± 1	± 1	± 1	± 1	± 1	± 1	± 1	± 1	± 1	± 1	± 1	± 1	± 3			
Hematology, biochemistry, urinalysis	X																		
Concomitant medications	X	X	X	X	X	X	X	X	X	X	X	X	X	X	X	X			
Adverse event collection	X	X	X	X	X	X	X	X	X	X	X	X	X	X	X	X			
BG and SMBG																			
Blood glucose samples during 4 hr PK ^e		X																	
Remind subject to obtain 7 Fasting SMBGs in week prior to Visit 2, PK		X																	
Dispense glucose meter, test strips ^f	X																		
Training on both the study supplied Glucose Meter and e-diary		X																	

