3 STUDY DESIGN

3.1 Overview of Study Design

MKC-TI-155 Part 1 will be a single-arm, multi-center, open-label, uncontrolled study to evaluate PK, safety, and ability to titrate AFREZZA[®] in children ages 4 to 17 years with T1DM, who were previously on a regimen of basal-bolus insulin therapy administered by multiple daily injections (MDI).

The structure of the study is as follows:

- Single dose PK at breakfast
- 4-week titration period starting at lunch after PK evaluation
- Optional 52-week safety extension

The screening period is up to 3 weeks. On Day 1, eligible subjects will receive a single dose of AFREZZA[®] prior to PK sampling. There will be 3 different doses of AFREZZA[®] for the PK study. The AFREZZA[®] dose (4, 8, or 12 units) will be based on the dose of SC RAA that the subject would usually receive for a breakfast containing a predetermined level of carbohydrate, comprising approximately 50% of the total caloric content. After this starting dose, each subject will be titrated with AFREZZA[®] TI according to the titration rules given in the protocol (2).

After the 4-week titration period, subjects will have the option to continue in a 52-week extension study at the Investigator's discretion. For subjects who opt not to continue treatment with AFREZZA[®], a follow-up visit will occur approximately 1 week after the end of AFREZZA treatment for safety assessments (duration of 1 day). For subjects who participate in the extension study, an end-of-study follow-up visit will be conducted 4 weeks after the 52-week treatment period.

The study will be conducted sequentially in age groups beginning with Cohort 1. Approximately 46 subjects will be enrolled sequentially into 3 age cohorts:

- **Cohort 1: 13 to 17 years;** approximately 18 subjects distributed across 4, 8, and 12 unit starting dose groups. Before proceeding to Cohort 2, at least 14 subjects must be dosed (i.e., must complete Visit 2). Of those, at least 6 subjects must receive the 8 unit dose.
- **Cohort 2: 8 to 12 years;** approximately 14 subjects distributed across 4 and 8 unit starting dose groups (the sample size may be adapted after taking the PK data from Cohort 1 into

account). Before proceeding to Cohort 3, at least 6 subjects must have completed Visit 15, and all subjects in Cohort 2 must have been evaluated for PK.

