8.1.1.2 Visit Window

Visit windows are defined for visit-specific parameters as following:

Table 2 Visit Window

Parameter	Study Period	Analysis Visit	Target Relative Day (s)*	Visit Window (Relative Days)*
HbA1c, Anti-insulin antibody	Screening	Screening	-21 to -7	[Day of ICF signed, - 1]
	Titration	Week 4 (Visit 15, EOT)	29	[22, 36]
	Extension	Month 12 (Visit 28, EOT)	Start day of the extension period + 365	[Start day of the extension period + 337, End day of the extension period + 393]
FEV ₁	Screening	Screening	-21 to -7	[Day of ICF signed, - 1]
	Titration	Day 1	1	No visit window, data collected on that day will be summarized by nominal time point
		Week 2 (Visit 9)	15	[8, 21]
		Week 4 (Visit 15, EOT)	29	[22, Treatment end day of the titration period]
		Follow-up	36	[Treatment end day of the titration period + 1, End day of the titration period]. Only subjects who opt not to participate in the extension period should have this visit.
	Extension	Month 3	Start day of the extension period + 91	[Start day of the extension period + 77, Start day of the extension period + 105]
		Month 6	Start day of the extension period + 183	[Start day of the extension period +169 , Start day of the extension period +197]
		Month 9	Start day of the extension	[Start day of the extension period +260, Start day of the extension period +288]

Parameter	Study Period	Analysis Visit	Target Relative Day (s)*	Visit Window (Relative Days)*
			period + 274	
		Month 12 (Visit 28, EOT)	Start day of the extension period + 365	[Start day of the extension period + 351 , Treatment end day of the extension period]
		Follow-up	Start day of the extension period + 396	[Treatment end day of the extension period +15, End day of the extension period]
Vital Signs and 7-Point SMBG	Screening	Screening	-21 to -7	[Day of ICF signed, - 1]
	Titration	Day 1	1 (for Vital Signs only)	No visit window, data collected on that day will be summarized by nominal time point
		Week 1 (Visit 5)	8	[5, 11]
		Week 2 (Visit 9)	15	[12, 18]
		Week 3 (visit 12)	22	[19, 25]
		Week 4 (Visit 15, EOT)	29	[26, Treatment end day of the titration period]
		Follow-up (for Vital Signs only)	36	[Treatment end day of the titration period +4, End day of the titration period]. Only subjects who opt not to participate in the extension period should have this visit.
	Extension	Month 3	Start day of the extension period + 91	[Start day of the extension period + 77, Start day of the extension period + 105]

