8.3.7 Vital Signs

Schedule and Parameters

Version Date: 17-Jan-2020

Vital signs assessments will be made at screening, at visits 2, 6, 9, 12, 15 and 16 in the titration period, and at visits 19, 22, 25, 28 and 29 in the extension period, as well as at the early termination visits in both periods. Height will be collected at screening only. The following parameters will be collected at all visits: respiratory rate, sitting blood pressure (systolic blood pressure and diastolic blood pressure), pulse rate, temperature, and body weight. At Visit 2, these parameters will be collected at two time points: pre-dose and post-dose.

All the measurements will be presented in international units. If measurements are collected in different units, a conversion will be made first before presentation. Below is the summary of conversion between different units.

Conversion	Formula
From lbs to kg in weight	Weight (kg) = Weight (lbs) x 0.45
From inch to meter in length	Length (meter) = Length (inch) x 2.5
From F to C in temperature	Temp (C) = {Temp (F) -32} x 5/9

Table presentation

For each parameter, descriptive statistics will be provided by cohort and analysis visit/time point. Change from baseline to all post-baseline visits/time points will be provided by cohort, except for height.

Subject Listings

Detailed information of every measurement will be listed, by (in the order of) cohort, investigator site, subject and visit/time point.

Graphical Presentation

For BMI, a Mean (SE) plot representing mean and SE for each cohort at each analysis visit will be provided.

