Listing 16.2.7.10	Hypoglycemic Events – Safety Population	X
Listing 16.2.7.11	Severe Hypoglycemic Events – Safety Population	X
Listing 16.2.7.12	Cough – Safety Population	X
Listing 16.2.8.1	Vital Signs – Safety Population	X
Listing 16.2.8.2	Physical Examinations – Safety Population	X
Listing 16.2.8.3	Spirometry Tests – Safety Population	X
Listing 16.2.8.4	Anti-insulin Antibody – Safety Population	X
Listing 16.2.8.5	Urine Cotinine Tests – Safety Population	
Listing 16.2.8.6	Female Reproductive Status -- Safety Population	
Listing 16.2.8.7	Pregnancy Tests -- Safety Population	
Other		
Listing 16.2.9.1	7-Point SMBG (eDiary Data) – Safety Population	
Listing 16.2.9.2	HbA1c – Safety Population	

Listing 16.2.9.3	Insulin to Carbohydrate Ratio – Safety Population	
------------------	---	--

List of Figures		Include in DMC
Treatment		
Figure 14.1.1.1	Average Daily total dose of AFREZZA [®] (eDiary Data) -- Safety Population	
Figure 14.1.1.2	Average Prandial Dose of AFREZZA [®] by Meal (eDiary Data) -- Safety Population	
Figure 14.1.1.3	Total Daily Post-Prandial Dose of AFREZZA [®] Over Time (eDiary Data) -- Safety Population	
Pharmacokinetic		
Figure 14.2.1.1	Mean of Baseline-Corrected Serum Insulin Concentrations Over Time by PK Dose of AFREZZA [®] – PK Population	X
Figure 14.2.1.2	Individual Patient Profile of Baseline-Corrected Serum Insulin Concentrations Over Time – PK Population	X
Figure 14.2.2.1	Mean of Serum FDKP Concentrations Over Time by PK Dose of AFREZZA [®] – PK Population	X
Figure 14.2.2.2	Individual Patient Profile of Serum FDKP Concentrations Over Time – PK Population	X
Figure 14.2.3.1	Mean of Blood Glucose Levels Over Time at PK Visit – PK Population	X
Figure 14.2.3.2	Individual Patient Profile of Blood Glucose Levels Over Time at PK Visit – PK Population	X
Safety		
Figure 14.3.1.1	Day Profile of Hypoglycemic Events – Safety Population	
Figure 14.3.1.2	Time Profile of Hypoglycemic Events in Relation to Pre-meal Dosing Time – Safety Population	
Figure 14.3.2.1	Day Profile of Cough – Safety Population	
Other		
Figure 14.4.1.1	Average SMBG by Meal and Time Point (eDiary Data) – Safety Population	
Figure 14.4.1.2	Mean of 7-Point SMBG (eDiary Data) – Safety Population	
Figure 14.4.1.3	Average of 7-Point SMBG by Time Point (eDiary Data) – Safety Population	

Figure 14.4.1.4	HbA1c – Safety Population	
Figure 14.4.2.1	BMI – Safety Population	

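### BMI at every visit uses the screening height, so the planned BMI figure overstates BMI in children who grow during the extension that the SAP defines

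*SAP*

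**What the plan says.** SAP section 5.10 defines BMI at a given visit as "Weight (in kg) measured at this visit/height (in m) measured at screening", the height being squared. SAP section 8.3.7 (Vital Signs) states: "Height will be collected at screening only". The protocol agrees: the section 1.1 flow chart places height in the screening examination ("Full physical examination including Tanner stage, body weight and height, body temperature"), and the later abbreviated examinations record body weight only.

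Weight is measured throughout. In the extension, section 8.3.7 schedules vital signs, including weight, "at visits 19, 22, 25, 28 and 29 in the extension period, as well as at the early termination visits in both periods". It then plans the figure: "For BMI, a Mean (SE) plot representing mean and SE for each cohort at each analysis visit will be provided". Appendix 3 lists this as Figure 14.4.2.1, "BMI – Safety Population".

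The analysis visits come from SAP Table 2 (section 8.1.1.2). For vital signs they are the titration visits, then Months 3, 6, 9 and 12 of the extension and a follow-up. The Month 12 target is "Start day of the extension period + 365". Section 3.1 describes the extension: after titration, "subjects will have the option to continue in a 52-week extension study".

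Neither document re-measures height, adjusts BMI for growth, or follows a BMI percentile or z-score over time.

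**The concern.** BMI is used to relate weight to current height. If the denominator is frozen at screening, each subject's BMI is that subject's weight times a constant, and the index carries no height information after screening. Subjects are 4 to 17 years old, and protocol section 4.1 itself notes that they pass through growth and puberty. Weight that accompanies ordinary growth in height would then appear as rising BMI.

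At stake is the reading of one figure. A mean curve that climbs through Month 12 invites a conclusion about adiposity that the data cannot support. The error also varies with each subject's growth, so differences between the cohort curves would partly reflect growth.

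**Working it through.** **No plan figure to reproduce.** The documents state no BMI value, so the check is of the formula.

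**Direction.** Let w be weight at the visit, h0 height at screening and h1 height at the visit.

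- Planned BMI = w / h0²
- BMI from same-day height = w / h1²
- Ratio = (h1/h0)², so the overstatement is (h1/h0)² − 1

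This is above zero whenever h1 > h0 and zero when there is no growth. Because h0 is constant within a subject, percent change in planned BMI equals percent change in w.

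**Elapsed time, from the SAP.**

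- Screening: Day −21 to Day −7, that is, 21 to 7 days before Day 1.
- Week 4: Day 29, so 28 + 21 = 49 days after a Day −21 screening.
- Extension start (section 5.4): the day after Visit 15, nominally Day 30. Month 12 is Day 30 + 365 = Day 395. That is 394 + 7 = 401 to 394 + 21 = 415 days after screening.

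**Growth, assumed.** The documents give neither heights nor growth rates, so both are varied: h1 = h0 + g × days / 365.25, with g in cm per year.

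Example: h0 = 105 cm and g = 7 give growth of 7 × 415 / 365.25 = 7.95 cm by Month 12, and (112.95/105)² − 1 = 15.7%.

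Overstatement at Month 12 (415 days), with Week 4 (49 days) in parentheses:

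| Screening height | 3 cm/yr | 5 cm/yr | 6 cm/yr | 7 cm/yr |
|---|---|---|---|---|
| 105 cm | 6.6% (0.8%) | 11.1% (1.3%) | 13.4% (1.5%) | 15.7% (1.8%) |
| 125 cm | 5.5% (0.6%) | 9.3% (1.1%) | 11.2% (1.3%) | 13.1% (1.5%) |
| 140 cm | 4.9% (0.6%) | 8.3% (1.0%) | 10.0% (1.2%) | 11.7% (1.3%) |
| 160 cm | 4.3% (0.5%) | 7.2% (0.8%) | 8.7% (1.0%) | 10.2% (1.2%) |

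For 105 to 140 cm the Month 12 range is therefore about 5% to 16%, and Week 4 stays under about 2%. On the BMI scale, assuming a true value of 17 kg/m², a 125 cm child growing 6 cm a year would be plotted 17 × 0.112 = 1.9 kg/m² too high at Month 12.

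**Which cohort is most affected.** For equal growth in cm the error is larger in shorter children, but growth need not be equal. An assumed 6 cm gained from 120 cm gives (126/120)² − 1 = 10.25%. An assumed 8 cm gained from 155 cm, as in a pubertal spurt, gives (163/155)² − 1 = 10.6%. The ordering of the cohorts follows the assumption.

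**The case against.** The strongest objection is that the material error lies entirely in an extension that the supplied protocol does not contain. Amendment 3 lists the PK day and the 4-week titration (section 6.1) with a 1-week follow-up (section 6.3). Its flow chart ends at Visit 16; the only trace of an extension is a footnote about test strips. The SAP is written to Amendment 2, as its reference list shows. This stands as a condition on the point. It does not remove it, because the SAP, dated 17-Jan-2020, still builds the extension into its design, study periods, visit windows and disposition categories, and tells the analyst to plot BMI there. The documents do not settle whether extension data will exist.

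Second, BMI over time is a minor output. It is not a named safety endpoint in SAP section 4.2, and Appendix 3 does not mark its figure for the DMC. Body weight and its change from baseline are already summarised by visit in Table 14.3.3.1, which is marked for the DMC. This stands, and it makes the remedy easy.

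A reader might also infer that the plot would show excess weight gain caused by treatment. The study is single-arm and uncontrolled, so a rising curve could not be attributed to treatment even with same-day height. The other tempting inference, that the youngest cohort must be worst affected, fails because the documents hold no growth data and plausible assumptions reverse the order.

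**Conclusion.** The point holds for the extension visits that the SAP defines. Followed as written, section 5.10 gives a BMI that is too high in every child who has grown since screening, and nothing else in either document corrects it. The direction needs no assumption about size. The figure of about 5% to 16% at Month 12 rests on assumed growth of 3 to 7 cm a year, assumed screening heights of 105 to 140 cm, and screening on Day −21. If only titration data exist, what remains is an error under about 2% on those assumptions, which is not worth pursuing.

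The documents do not support reading this as a flaw in the trial's safety conclusions. It affects one descriptive figure, and no PK or main safety conclusion depends on it. The priority is low, but the correction is simple.

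**What to change.** In SAP section 8.3.7, limit Figure 14.4.2.1 to screening and the titration visits, and refer to the body-weight summaries in Table 14.3.3.1 for the extension. This is a text edit with no new data or tables.

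If BMI is kept at extension visits, label it as weight scaled by screening height and state that it is not to be interpreted as change in adiposity. This costs a title and a footnote.

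Measuring height at extension visits would also remove the error, but it is a change to study procedures and cannot recover heights for visits already past, so it is not the main recommendation.

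Separately, reconcile the SAP with the protocol on whether the extension is part of this study; that determines whether the Month 3 to Month 12 analyses are needed at all.
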